The recruitment of participants will occur at the University of Uyo, Uyo, Akwa-Ibom State. Specifically, healthy female students studying at the University will be recruited for this study. The recruitment process will involve all the departments within the Town Campus and Annex Campus of the University. The contact details of the class representatives of each level in each department within the aforementioned campuses will be obtained. The recruitment invitation for the study will be posted on the WhatsApp group page of each class by their class representative. In addition, flyers will also be distributed throughout the classrooms and hostels. A referral incentive of N100 per three referrals will be added to the recruitment invitation. The potential participants will be attended to by two experienced and trained research staff who are accustomed to all the study procedures. Participants who meet the preliminary eligibility criteria (living in the university hostel or living in close proximity to the university) and state clear interest in study participation, will then be invited to voluntarily complete the screening questionnaire and informed consent process.

Eligibility, informed consent, and enrollment processes

The participants who meet all the pre-screen requirements will be taken through the enrollment process, which includes eligibility for the study by filling out a questionnaire; filling out and signing the informed consent form; and measurement of their vitals (temperature, pulse rate, respiration, blood glucose level, and blood pressure). All participants that meet all the requirements for this stage will be considered fully enrolled for the study.

Eligibility criteria

Inclusion criteria are as follows:

(1) Age between 18 and 26; (2) Non-habitual coffee and tea drinkers who consume coffee, green tea, or black tea 2-5 times in the last two months; (3) Non-allergic to coffee, green tea, black tea, or honey; (4) Absence of medication use; (5) Will refrain from ingesting energy drinks, carbonated beverages, caffeinated beverages, or food for 24 hours before the study and throughout the study periods; (6) Will not consume anything except water after 11 p.m. during the experimental days;
 (7) Will be available and cooperate throughout the study duration.

Exclusion criteria are as follows:

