Presence of cardiovascular disorders, hypertension, or diabetes; (2) Blood pressure above 120/80 mmHg and random blood glucose above 125 mg/dL; (3) Alcohol intake; (4) Smoking; and (5) Habitual coffee or tea drinkers.

Randomization

Participants who meet the eligibility criteria, possess medically acceptable vital signs, and submit a signed informed consent form will undergo randomization conducted by research staff. A simple randomization method will be employed. Each group will be assigned a distinct number, which will be inscribed on slips of paper corresponding to the total number of participants. Each slip, bearing one of the assigned group numbers, will be securely folded. These will then be put in a basket, which will be thoroughly jostled. All these procedures will be executed by a trained research personnel. Each participant will have the opportunity to randomly select one slip of paper. The selection process will be overseen by another research staff member who is not involved in the initial phase. The group number selected by each participant will determine their assigned group.

Compensation

At the end of the study, the participants will be compensated for cooperating and following through with all the research procedures. A token of one thousand naira will be given to each participant.

Safety considerations

This study involves healthy participants, and all the procedures involved in this study are generally safe, with minimal risks. To ensure the safety of the participants, all the parameters will be measured by well-trained and experienced research personnel. However, if any unfavorable or unintended sign or symptom arises, it will be noted as an adverse event. All research personnel will be trained to recognize, document, and report adverse events.

Follow-up

Although the study involves healthy participants and the study procedures are generally safe, the participants will be followed up via a phone call. All the participants will be requested to give their contact details and those of their family and friends. The follow-up call will be made twice (3 days and 10 days after the completion of the study). If an adverse event is recorded, a follow-up visit will be arranged with the participant to ensure their well-being.

Data management and quality control

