
 Type
 2
 Diabetes.
 Research
 Journal
 of
 Pharmacognosy.,
 2024,
 11(3),
 31-40.

 10.22127/RJP.2024.418824.2239

23. Saha S. Honey-the natural sweetener become a promising alternative therapeutic: a review.South Indian Journal of Biological Sciences 2015; 1(2): 103.

24. Charan, J., & Biswas, T. How to calculate sample size for different study designs in medical research?. Indian journal of psychological medicine., 2013, 35(2), 121–126. https://doi.org/10.4103/0253-7176.116232

PARTICIPANT ELIGIBILITY QUESTIONNAIRE

Personal information

1. What is your name?

- 2. Gender? M / F
- 3. How old are you?

[] Less than 18 years [] 18-26 years [] 26 years and above

- 4. Weight: _____
- 5. Height: _____
- 6. Phone number:

Medical history

- 7. Do you have a history of hypertension (high blood pressure)? (Yes/No)
- 8. Do you have a history of diabetes or impaired glucose tolerance? (Yes/No)
- 9. Do you have any cardiovascular problem? (Yes/No)

If yes, please specify:

10. Are you on any medication? (Yes/No)

If yes, please specify the medication(s):

Lifestyle

- 11. Do you smoke? (Yes/No)
- 12. Do you consume alcohol? (Yes/No)
- 13. Are you currently following any specific diet plan? (Yes/No)

If yes, please provide details:

Dietary Habits

14. How often do you consume coffee/black tea/green tea?

[] Daily [] Several times per week [] Occasionally [] Rarely/Never

15. Do you regularly consume honey as a sweetener? (Yes/No)

16. Do you have any known allergies or intolerances to any of the following? (Yes/No)

[] Honey

- [] Coffee
- [] Black tea
- [] Green tea

General Health

17. Have you been diagnosed with any chronic medical conditions? (Yes/No) If yes, please provide details:

- 18. Are you currently pregnant or breastfeeding? (Yes/No)
- 19. Have you undergone any recent surgeries? (Yes/No)

If yes, please specify:

20. Are you willing to comply with the study protocol, including the consumption of the assigned tea for the specified duration? (Yes/No)

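### Does the screening form need a two-month count of coffee and tea use, and does the loose joining word in exclusion 2 need changing, for the trial's results to stand?

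*Combined protocol and SAP*

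**What the plan says.** All references are to the combined protocol and SAP.

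- **Eligibility criteria, inclusion 2:** "Non-habitual coffee and tea drinkers who consume coffee, green tea, or black tea 2-5 times in the last two months".
- **Eligibility criteria, exclusion 5:** "Habitual coffee or tea drinkers". No number defines the term.
- **Participant eligibility questionnaire, item 14:** "How often do you consume coffee/black tea/green tea", with the answers "Daily [] Several times per week [] Occasionally [] Rarely/Never". The three drinks are pooled in one question.
- **Eligibility criteria, exclusion 1:** "Presence of cardiovascular disorders, hypertension, or diabetes".
- **Eligibility criteria, exclusion 2:** "Blood pressure above 120/80 mmHg and random blood glucose above 125 mg/dL".
- **Eligibility, informed consent, and enrollment processes:** enrolment is a sequence "which includes eligibility for the study by filling out a questionnaire", followed by consent and measurement of vital signs, which include blood pressure and glucose.
- **Recruitment and screening:** "The potential participants will be attended to by two experienced and trained research staff".
- **Randomization:** only volunteers who satisfy the criteria, have acceptable vital signs (no limits given) and have signed consent go on to draw a group slip.

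**The concern.** Inclusion 2 is a numeric rule with a lower and an upper bound over a fixed look-back period. Item 14 asks for neither a number nor a period. A volunteer who ticks *Occasionally* may be inside or above the range, and one who ticks *Rarely/Never* may be inside or below it. A later report could not prove from the form that its participants were the light users the protocol describes.

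Exclusion 2 raises a similar doubt. Read literally, it removes only people above both limits. Read as a list, it removes anyone above either. Exclusion 1 gives no thresholds, and the vital-sign condition in Randomization gives none either, so the text does not settle the point and two staff members could in principle decide differently about the same volunteer.

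Blood pressure and glucose are study outcomes, and caffeine is a constituent of the drinks under study. If these rules failed in a way that differed between groups, the comparisons would be at risk. If they failed equally in all groups, the risk would be confined to describing and reproducing the population.

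**Working it through.** There is no stated figure to reproduce. The check is of the text, with small sums where they help.

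**1. What item 14 can and cannot separate.** Two months is about 61 / 7 = 8.7 weeks. The permitted range is therefore 2 / 8.7 = 0.23 to 5 / 8.7 = 0.57 uses a week.

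| Habit | Uses in two months | Against 2 to 5 | Plausible answer |
|---|---|---|---|
| Never | 0 | below | *Rarely/Never* |
| Monthly | 2 | inside | *Rarely/Never* |
| Fortnightly | 8.7 / 2 = 4.4 | inside | *Occasionally* |
| Weekly | 8.7 | above | *Occasionally* |

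The two most frequent categories lie well above 0.57 a week, so item 14 rejects those drinkers correctly. It leaves weekly against fortnightly use, and none against two uses, unresolved.

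**2. Whether the count is otherwise lost.** Inclusion 2 remains a condition of randomisation whatever the form asks. The questionnaire is one component of enrolment and is not a one-to-one checklist. It asks about pregnancy, surgery and diet plans, which are not listed criteria, and it has no specific item for the fasting rules in inclusions 5 and 6, only the general compliance question (item 20). Trained staff attend to the volunteers and can ask for the number. Inclusion 5 also bars caffeinated drinks for 24 hours beforehand and throughout the study. This does not verify the count and says nothing about tolerance, but it limits carry-over from recent intake.

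**3. Total or per drink.** A per-drink reading would raise the ceiling to 3 x 5 = 15 uses, or 15 / 8.7 = 1.7 a week. That fits poorly with a population described as non-habitual, and item 14 pools the drinks. A single total is the natural reading.

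**4. Exclusion 2.** Exclusions 1 and 5 use *or* between alternatives, which keeps the literal reading alive. Against that, the exclusion list itself places *and* before its fifth entry, where the word plainly does not require all five conditions together.

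The documents give no prevalences, so the numbers affected cannot be derived. As an illustration only, let p be the share above the blood pressure limit and q the share above the glucose limit, assumed independent. Under the literal reading, the share of those enrolled who are above one limit only is [p(1 - q) + q(1 - p)] / (1 - pq).

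- p = 0.10, q = 0.01: 0.108 / 0.999 = 0.108, and 0.108 x 70 = 7.6 people.
- p = 0.30, q = 0.10: 0.340 / 0.970 = 0.351, and 0.351 x 70 = 24.5 people.

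Exclusion 1 and the vital-sign condition would lower these, possibly to none. Under the list reading the answer is 0. A span of 0 to about 25 of 70, resting wholly on assumed inputs, says little. Both quantities are measured at enrolment and again at 0 minutes, so the data themselves would show how many participants exceeded either limit.

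**5. Consequence for the analysis.** Screening comes before the slip is drawn, so whoever is admitted is allocated at random. A looser or tighter gate changes who is in the trial, not which group they join. A wider mix of people could increase the spread of outcomes, but the ANOVA estimates that spread from the data. No planned power is upset, because the Sample size section puts no values into its formula and sets 70 on funds, equipment, manpower and data from the literature.

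**The case for a change.** The best case for a change is that it is cheap. One reworded item would capture three counts, and one clarified sentence would settle exclusion 2. Other criteria do have matching questions: items 7 to 9 for exclusion 1, item 10 for medication, items 11 and 12 for smoking and alcohol, item 16 for allergy. The intake rule is the odd one out, and it is how the protocol limits prior exposure to the drinks. Relying on staff to ask leaves no written record that they did.

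Part of this stands. The form alone cannot document compliance with either bound, and the wording of exclusion 2 is loose. A careful report would describe the participants by their item 14 answers and their screening measurements, and would not assert that the two-month count was verified.

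The rest does not carry through to the results. No outcome consequence is identified for a weekly drinker admitted in place of a fortnightly one, and a recalled two-month count has error of its own. The change may also come too late: Study design dates the work to July to October 2023, while the reference list includes 2024 papers, so screening may be over. If it is, rewording the form recovers nothing.

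**Conclusion.** The observation is accurate, but no change to the plan follows. Item 14 omits a detail that screening staff can supply by asking, and exclusion 2 is a wording slip whose two readings affect who enters the trial and not the validity of the group comparisons. Which reading is intended is for the investigators to state. Exclusion 2 and the unquantified vital-sign condition need to be reconciled so that every volunteer is treated alike, but that is a matter of editing the text and not of design or analysis.

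The effect on bias in the randomised comparisons is nil, given that eligibility is decided before the draw, as the Randomization section provides. The effect on the description of the population is real but small: the form leaves adjacent light-use habits indistinguishable while still screening out frequent drinkers. The number enrolled above one exclusion 2 limit is unknown, and the range of 0 to about 25 of 70 depends on assumed prevalences and independence, so it should carry no weight.

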Methods: The study will be conducted over a 3-day period, involving healthy young female adults. The participants will be randomly assigned to seven groups: Control (250 mL of warm water); Coffee Group (2.25g of coffee per 250ml of hot water); Honey-sweetened coffee group (2.25g of coffee per 250 mL of hot water with 20 mL of honey); Black tea group (2g black tea diffused in 250 mL hot water); Honey-sweetened black tea (2g black tea diffused in 250 mL hot water with 20 mL honey; Green Tea group (2g green tea diffused in 250 mL hot water); and Honey-sweetened green tea group (2g green tea diffused in 250 mL hot water with 20 mL honey. The basal measurements of each participant will be taken, after which the participants will be given their designated beverages. The blood pressure and heart rate of each participant will be measured at 15, 30, 45, and 60 minutes, and blood glucose at 30 and 60 minutes after consumption.

Discussion: This research aims to provide significant insights regarding the possible health benefits or risks linked to the consumption of coffee, black tea, green tea and honey-sweetened coffee, black tea, and green tea . It will specifically focus on their effects on critical physiological factors such as blood pressure, heart rate, and blood glucose level. Understanding these factors is essential for maintaining individual health, as any adverse changes in them can lead to detrimental health consequences. By examining the relationship between these beverages and these vital health indicators, the study seeks to contribute to the broader understanding of dietary influences on cardiovascular and metabolic health.

Keywords: Coffee, Black tea, green tea, Honey-sweetened coffee, Honey-sweetened tea, Blood pressure, Heart rate, Blood glucose

Introduction

Coffee and tea stand out as globally favoured and versatile beverages of choice. Their nutritional significance primarily derives from their bioactive constituents. Coffee and tea are enriched with different polyphenols, known for their wide array of biological functions, encompassing antioxidant capabilities, potential cancer prevention, inflammation suppression, and protective properties against conditions like cardiovascular diseases, diabetes, hyperlipidemia, and obesity [1]. The polyphenols in coffee are chlorogenic acid, diterpenes, and trigonellin, while those in tea are catechins [2]. The catechins in green tea are epigallocatechin-3-gallate, gallocatechingallate,

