The study is an experimental study; specifically, it is a randomized controlled trial that will involve healthy young female adults between the ages of 18 and 26 years. The participants will consume honey-sweetened black tea, green tea, and coffee, or plain black tea, green tea, and coffee, or warm water, one cup a day for 3 days. The study will be carried out in the Physiology Laboratory, University of Uyo, and will be done within the period of July to October 2023. Each participant will fill out a consent form prior to the study, after which the participants will be given the beverages and observed for 60 minutes, during which their blood pressure, heart rate, and blood glucose level will be measured. This procedure will be repeated for the 3 days of the study. Prior to the consumption of the beverages, baseline measurements of blood pressure, heart rate, and blood glucose will be taken. For this study, a minimum of 200 volunteers will be recruited, and out of this, the eligible participants will be selected.

Methodology

The randomized controlled trial will be carried out among female students studying at the University of Uyo. The participants will be randomly grouped as follows:

Group 1 (Control) will be given 250 mL of water.

Group 2 (Coffee group) will be given 2.25 g of coffee per 250 mL of hot water.

Group 3 (Honey-sweetened coffee group) will be given 2.25 g of coffee per 250 mL of hot water with 20 mL of honey.

Group 4 (Black tea group) will be given one tea bag (2 g) per cup (250 mL) of hot water.

Group 5 (Honey-sweetened black tea) will be given one tea bag (2 g) per cup (250 mL) of hot water with 20 mL of honey.

Group 6 (Green tea group) will be given one bag (2 g) per cup (250 mL) of hot water.

Group 7 (Honey-sweetened green tea) will be given one bag (2 g) per cup (250 mL) of hot water with 20 mL of honey.

Study procedure

• Participants will be screened for eligibility criteria and will be provided with informed consent to participate in the study.

• The participants will be divided into seven groups, as specified above, through random allocation.

• After arrival, the subjects will be allowed to rest for 30 minutes. Then, baseline measurements of their blood pressures, heart rates, and blood glucose levels will be taken. This will serve as the 0-minute measurement. The subjects will then be given the standardized drinks according to their groups.

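### Inclusion criteria (5) and (6), as written, do not set one workable fasting rule for the three glucose visits

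*Combined protocol and SAP*

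**What the plan says.** All references are to the combined protocol and SAP.

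- **Eligibility criteria, inclusion (5):** the participant "Will refrain from ingesting energy drinks, carbonated beverages, caffeinated beverages, or food for 24 hours before the study and throughout the study periods".
- **Eligibility criteria, inclusion (6):** the participant "Will not consume anything except water after 11 p.m. during the experimental days".
- **Abstract, Methods:** "The study will be conducted over a 3-day period". **Study design:** participants are "given the beverages and observed for 60 minutes", and "This procedure will be repeated for the 3 days of the study".
- **Study procedure:** "After arrival, the subjects will be allowed to rest for 30 minutes". Baseline readings and the drink follow. Glucose is taken at 0, 30 and 60 minutes. No clock time and no check on last food is given.
- **Participant eligibility questionnaire:** no item asks about last food. The compliance item reads "Are you willing to comply with the study protocol, including the consumption of the assigned tea for the specified duration", which names the drink but not the fast.
- **Exclusion (2):** a blood pressure limit of 120/80 mmHg and a random glucose limit of 125 mg/dL, joined by *and*.
- **Statistical analysis:** one-way and two-way ANOVA with Tukey comparisons. The factors are not named.

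**The concern.** Blood glucose is named in the primary aim, and one objective asks what three days of consumption do to it. Glucose before and after a drink depends on time since food, so the fasting state should be the same at each visit and clear to staff and participants.

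The two criteria point in different directions. Criterion (5) lists food among the things barred before and throughout. Criterion (6) sets an evening cut-off, which has a purpose only if eating is allowed earlier that day. Two things are at stake:

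- **Noise.** Participants or staff who follow different readings would arrive in different fasting states.
- **Comparability of days within an arm.** If visit 1 follows a different fast from visits 2 and 3, a change in glucose across days may reflect the fast and not the drink, unless it is set against the change in the water arm over the same days.

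Exclusion (2) has a similar drafting fault: read literally, it removes only volunteers who exceed both limits.

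**Working it through.** The plan states no fasting duration, so there is no figure to reproduce. The check sets the two criteria side by side and works out what each reading implies.

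**Inputs from the protocol.** 24 hours and the span of the ban (inclusion 5); the 11 p.m. cut-off (inclusion 6); three daily visits (Abstract, Study design).

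**Assumptions.** Consecutive days, and the same arrival time *s* (24-hour clock) each day. The protocol gives no arrival time; 8 a.m. to 2 p.m. is used for illustration.

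**Formula.** Hours from 11 p.m. to arrival = *s* + 1. At 8 a.m. this is 9 h; at 2 p.m. it is 15 h.

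**Minimum hours since food at arrival, study drink aside:**

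| Reading | Visit 1 | Visit 2 | Visit 3 |
|---|---|---|---|
| A. (5) taken literally throughout | 24 | 24 + 24 = 48 | 24 + 48 = 72 |
| B. (5) governs visit 1, (6) the later visits | 24 | 9–15 | 9–15 |
| C. (5) covers only caffeinated food; (6) covers the evenings of days 1 to 3 | not set | 9–15 | 9–15 |
| D. Water only from 11 p.m. on the night before every visit | 9–15 | 9–15 | 9–15 |

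Under B, visit 1 exceeds the later visits by 24 − (*s* + 1) = 23 − *s* hours: 15 h for an 8 a.m. arrival and 9 h for 2 p.m. A window of 7 a.m. to noon would give later fasts of 8 to 13 h and a gap of 16 to 11 h. The pattern does not depend on the window; the hours do.

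Under C, the evenings of days 1, 2 and 3 precede visit 2, visit 3 and no visit. The evening before visit 1 falls outside the experimental days.

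Only D gives the same rule at all three visits. It is probably what was meant, but neither criterion says it. The span named in (5), *study periods*, is undefined and could mean the whole three days or the observed sessions. The only glucose condition stated anywhere is *random*, at screening.

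**Exclusion (2), illustrative volunteer.** Take 135/85 mmHg with random glucose 100 mg/dL. Blood pressure is over its limit (135 > 120, 85 > 80) and glucose is not (100 < 125). With *and*, criterion (2) does not exclude her; with *or*, it does.

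**The case against.** The strongest reply is that this is loose drafting. The criteria are not strictly incompatible. The word *caffeinated* can be read to cover food as well as beverages, *study periods* can mean the sessions, and the cut-off in (6) is itself evidence that (5) was never meant as a total ban. Trained staff handle participants and would presumably give one instruction. The consent pages, where a fasting instruction might appear, are not in the copy reviewed. All of this stands as an account of probable intent. It does not supply the rule: even the favourable reading of (5) leaves the night before visit 1 uncovered.

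A reader might go further than the documents allow in four ways:

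- **Biased between-arm results.** Not supported. The wording applies equally to all seven randomised arms, each day has its own baseline, and a water control runs concurrently.
- **A real multi-day starvation regimen.** Reading A is the literal text, but (6) presupposes eating, so it cannot be taken as the intent. The weight of this point does not rest on the 48 and 72 hours.
- **A loss of power.** The protocol gives no standard deviation for glucose and no effect of fasting time, so no figure can be derived.
- **No screen for raised pressure or glucose.** Exclusion (1) bars hypertension and diabetes, vital signs are measured at enrolment, and they must be judged acceptable before randomisation.

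On exclusion (2), it is fair to say that *and* may be only a list connector, as it is between the last two exclusions. *Or* is very probably meant. But the questionnaire asks about hypertension and diabetes as history, and the requirement for acceptable vital signs states no limit, so the threshold itself should be written correctly.

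**Conclusion.** The point holds at a modest level. As worded, inclusion (5) and (6) do not give one workable fasting rule for the three glucose visits, and the night before visit 1 is not clearly covered. The consequences are possible added variability in glucose and a visit 1 fasting state that may differ from visits 2 and 3: by 9 to 15 hours under reading B with arrival assumed between 8 a.m. and 2 p.m., and by an unknown amount under reading C.

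This matters for any day-to-day comparison within an arm. The Statistical analysis section neither plans one explicitly nor rules one out. Comparisons between arms are not biased by it. Exclusion (2) is a separate, smaller wording error.

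The conclusion rests on the visible text and on consecutive visits. Wording in the removed consent pages could settle the fasting rule in practice, but the criteria would still need correcting.

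**What to change.** 1. **Inclusion (5):** limit it to energy, carbonated and caffeinated drinks (and caffeinated food, if intended), from 24 hours before visit 1 to the end of visit 3.
2. **Inclusion (6):** replace it with: only water after 11 p.m. on the night before each of the three visits, including the first.
3. **Visit form:** record time of last food at each visit.
4. **Exclusion (2):** reword as systolic above 120 or diastolic above 80 mmHg, or random glucose over 125 mg/dL.

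Before the first visit, the cost is rewording three criteria and adding one line to the form, giving 70 × 3 = 210 short entries. No change to sample size, arms or analysis is needed.

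The protocol says the study "will be done within the period of July to October 2023", and its reference list contains items dated 2024, so sessions may already have been run. In that case, state in the report the fasting and exclusion rules actually applied, and say so if the fast differed between visit 1 and the later visits. Any within-arm change across days should then be set against the change in the water arm.

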• Blood pressures and heart rates of the subjects will be measured and recorded 15 minutes, 30 minutes, 45 minutes, and 60 minutes after consumption of the drinks, while blood glucose levels of the subjects will be measured and recorded 30 minutes and 60 minutes after consumption.

• Blood pressure and heart rate will be measured using a digital sphygmomanometer. Blood pressure is measured in millimeters of mercury (mmHg) and recorded with the systolic number first, followed by the diastolic number. Heart rate is measured in beats per minute (bpm).

• Blood glucose level will be measured with a glucometer. Blood glucose level will be measured in mg/dL.

Intervention

Coffee, black tea, green tea, and honey

The coffee that will be used for this study is Nescafé Gold Blend, manufactured by Nestlé Coffee Brand, Nestlé Global, Vevey, Switzerland. The black tea is Lipton Yellow Label Black Tea, manufactured by Lipton Teas and Infusions, Rotterdam, Netherlands, and the green tea is Qualitea Natural Green Tea, packed by Qualitea Ceylon (PVT) LTD, Wattala, Colombo, Sri Lanka. These will be obtained from Market Square, Ibom Tropicana Mall, Uyo, Akwa-Ibom State, Nigeria. Raw dark amber honey produced by Apis mellifera adansonii will be used for this study, and it will be obtained from Vika Farms located in Mbak Etoi, Akwa-Ibom State, Nigeria.

The participants will be given a cup per day for 3 days. A tea cup will be prepared by infusing a tea bag in 250 mL of hot water (95°C for black tea and 80°C for green tea). The infusion will be done for 7-10 minutes with constant stirring. A cup of coffee will be prepared by dissolving 2.25 g of instant coffee in 250 mL of 95°C water with proper stirring.

The water will be allowed to boil and cooled down to a respectful temperature before the addition of either a tea bag or coffee. The beverages will then be allowed to cool to approximately 35 degrees before honey is added and given for consumption. The control group will be given 250 mL of water at 35°C.

Measurement of blood pressure, heart rate, blood glucose

Blood pressure and heart rate will be recorded on the left arm using an automated blood pressure monitor (Shanghai Little Doctor Electronics CO. LTD, Nantong 226007, China). First, the cuff

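### Nothing in the plan stops drink lining up with test session, clock time or device; drawing the slips by session would close the gap cheaply, although the slip draw itself is unbiased

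*Combined protocol and SAP*

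**What the plan says.** **Allocation.** The Randomization section states: "A simple randomization method will be employed". Group numbers go on slips, "which will be inscribed on slips of paper corresponding to the total number of participants". "These will then be put in a basket, which will be thoroughly jostled", and then "Each participant will have the opportunity to randomly select one slip of paper". Session, date, time of day and device are not mentioned.

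**Testing.** The abstract says "The study will be conducted over a 3-day period, involving healthy young female adults". The Study design section gives a July to October 2023 window. Study procedure has a 30-minute rest and a 0-minute measurement, after which "The subjects will then be given the standardized drinks according to their groups". Cuff readings follow at 15, 30, 45 and 60 minutes, and glucose at 30 and 60. No clock time or number of women per session is given.

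**Devices.** The measurement section says "Blood pressure and heart rate will be recorded on the left arm using an automated blood pressure monitor", with each reading taken three times and averaged. One make of monitor and one of glucometer are named. The number of units, and how women are assigned to them, are not stated.

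**Fasting.** Inclusion criterion 6 reads "Will not consume anything except water after 11 p.m. during the experimental days". Criterion 5 separately bars food for the 24 hours before the study and throughout it.

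**Analysis.** One-way and two-way ANOVA with Tukey comparisons at P < 0.05. The factors of the two-way model are not named, and no session, device or baseline term is stated.

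**The concern.** Blood pressure, heart rate and glucose can vary with time of day and length of fast, and readings can vary with the device. Under the 11 p.m. rule, a later test time means a longer fast. If the 70 women are tested in successive sessions, anything shared by a session moves all its members together. Where a session holds mostly one drink, that shared movement cannot be told apart from the drink's effect in a comparison of raw levels.

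The plan has no safeguard at any of the three points where one could sit: the draw, the timetable or the model. Nor does it require session, start time or device to be recorded, so a reader could not check afterwards whether drink and session were mixed.

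**Working it through.** **Inputs.** From the documents: N = 70, seven groups, five cuff time points in triplicate, three glucose time points, alpha 0.05. Assumed: 10 women per group (70 / 7; slips per group are not stated), the session shifts, and minutes per triplicate. The sample-size formula has no values for SD or difference, so 70 cannot be reproduced; the checks below need only N and the number of groups.

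**1. Are sessions likely?** If all 70 are tested on the same three days, each day needs 70 × 5 × 3 = 1,050 cuff readings and 70 × 3 = 210 finger pricks. If a triplicate takes 3 to 5 minutes (assumed), one monitor serves 15/5 = 3 to 15/3 = 5 women per 15-minute cycle.
- One monitor: 70/5 = 14 to 70/3, rounded up to 24, sessions. At about 75 minutes each (assumed), that is 17.5 to 30 hours.
- Four monitors: 70/20 to 70/12, rounded up to 4 to 6 sessions.

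**2. Session independent of drink.** Suppose half the women are in each of two sessions whose levels differ by s within-session SDs, and session is left out of the model. The extra variance is s²/4, so the standard error grows by √(1 + s²/4). False-positive rates come from 40,000 simulated trials with no drink effect.

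| s (assumed) | SE ratio | False positives, session ignored | False positives, blocked by session with session in model |
|---|---|---|---|
| 0.25 | 1.008 | 4.9% | 4.9% |
| 0.5 | 1.031 | 4.8% | 4.8% |
| 1.0 | 1.118 | 4.9% | 5.0% |

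The false-positive rate is therefore not at issue here. Chance imbalance is common, however. A given pair of groups differs by 4 or more women out of 10 in session membership in 12% of draws, and the largest gap among the seven groups is 4 or more in 71%. A gap of 4 in 10 moves a group difference by 0.4 × s, that is 0.10, 0.20 or 0.40 SD.

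**3. One drink per session, raw levels analysed.** Let r be the between-session SD divided by the between-person SD. With 10 per group, the F statistic is scaled by 1 + 10r². The critical value F(6, 63) is 2.246, so the true false-positive rate is P(F > 2.246 / (1 + 10r²)).

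| r (assumed) | 1 + 10r² | 2.246 / (1 + 10r²) | False-positive rate |
|---|---|---|---|
| 0.1 | 1.1 | 2.042 | 7% |
| 0.2 | 1.4 | 1.605 | 16% |
| 0.25 | 1.625 | 1.382 | 24% |
| 0.5 | 3.5 | 0.642 | 70% |

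Simulation agrees at r = 0.25 and 0.5 (24% and 70%).

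**4. Two sessions split by drink** (three drinks in one, four in the other). The simulated false-positive rate is 9%, 26% and 86% for shifts of 0.25, 0.5 and 1.0 SD.

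**The case against.** The strongest reply is that the basket draw is sound. A reader might infer that drawing all slips from one basket makes session or device differences appear as drink effects. It does not: step 2 shows that the ANOVA error term covers chance imbalance and the rate stays near 5%. That part of the reply stands in full.

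The 7% to 70% figures also need a timetable that no section contains. Preparation does not force one. There are only three brews; coffee and black tea share 95°C water, and the plain and honey versions share a brew. Convenience might favour grouping by brew, but hardly seven single-drink sessions. This stands as well, so those figures are conditional on conduct that the plan leaves open. Step 4 shows that a coarser grouping by drink would still matter.

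The load is partly assumed. The number of devices is not given, N was chosen with equipment and manpower in mind, and the four-month window would allow small cohorts at one fixed hour on different dates. Length of fast need not then vary. Date and device still could.

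Finally, a reader might conclude that a session shift could never be removed. A stable offset would cancel in change from the same-day 0-minute value, which is collected. The plan does not commit to analysing change, however, and a shift that alters within the hour would remain.

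**Conclusion.** The point holds as a gap in the design and analysis, and one that should be closed. The documents do not show that the trial is biased. Nothing in the plan prevents drink lining up with session, clock time or device, and nothing in the stated model would adjust for it.

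If sessions are independent of drink, the loss is precision (standard errors about 1% to 12% larger for shifts of 0.25 to 1.0 SD) and frequent chance imbalance. If testing were scheduled by drink and raw levels compared, false positives could reach 7% to 70% with one drink per session, for session SDs of 0.1 to 0.5 of the person SD. The shift sizes, 10 per group and the half-and-half split are assumptions; the documents give no values for them.

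Separately, the water-only rule after 11 p.m. and the 24-hour food rule do not fit together, so the intended length of fast cannot be read from the plan.

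**What to change.** - **Randomization:** keep the slips but draw by session. Put one slip of each group number in the basket for a session of seven women, or two of each for fourteen, so that every session has all seven drinks. Seventy women make 10 sessions of seven or 5 of fourteen. Let the women in a session draw only after all of them are enrolled and booked.
- **Study procedure:** state test times, session size and number of devices. Say that testing is not scheduled by drink. Keep each woman on the same start time, monitor and glucometer on all three days, and do not assign devices by group. Record session, start time and device.
- **Statistical analysis:** include session as a block and the same-day 0-minute value in the model.
- **Eligibility criteria:** reconcile the two fasting rules.

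Cost: no extra participants or measurements. Every drink must be ready in each session. At the assumed 3 to 5 women per monitor, seven women at once need two to three monitors and fourteen need three to five; the number available is not stated. No-shows leave incomplete sessions, and the last slip in a session is predictable, which drawing only after enrolment and booking makes less harmful.
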